Optimization Scans: In order to optimize the study MRI protocol, we will implement optimization scans with healthy volunteers (18-65 y-o) who will only undergo ~1-hour optimization scans including the non-invasive MRI scan (which is to be optimized for the study intervention scans). We have included a separate consent form for the optimization scan volunteers. Optimization scans will be conducted with healthy population (18-65 y-o).

Interventions. YB protocol will incorporate a set of yogic breathing practices that will create larger

modulations in CSF dynamics. Active control protocol will include slow breathing. Both 8-week interventions will consist of 60-minute weekly group on-site sessions (1 day/week) with a 20-minute daily home sessions (in between on-site sessions; 6 days/week) using home-aid practice materials. We will define a benchmark of at least 8 on-site sessions and 15-min daily^{13,14} home practice (4 days/week) in order to see the effects we propose. We will objectively track subjects' respiration using a wearable device, e.g., Spire¹⁵ or Oura ring¹⁶. We plan to buy one of each and pilot each for 2 weeks on several study team members to assess prior to the interventions. In addition, subjects will be instructed to report the frequency and duration of their daily home practice in a logbook provided. We have tested the Spire³ health tag and Fitbit tracker, and plan to include in the protocol to objectively determine subjects' home practice. Participants may have one or both of these devices for the study team to track participant's home practice.

Interventionists. The YB and the control intervention will be guided by two separate certified experienced yoga teachers. Prior to being involved in the study and guiding the study interventions, the two interventionists will go through the necessary trainings for human subject research and IRB protocol.

Outcome measures will be i) blood pressure, ii) body mass index (BMI), iii) CSF flow velocities measured with the non-invasive MRI technique during ~1-hour MRI scans, iv) physiological data from wearable devices. We will also review response to self-report questionnaires.

5) Study Population

a) Number of Subjects

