Post-acquisition, each data set will be examined for quality and completeness by the trained study team.

CSF flow:

- CSF flow data analysis will be performed using a semiautomated pulsatility-based segmentation procedure. The velocity waveform will be averaged over the highly correlated ROI pixels. The maximum and minimum peak values of the averaged CSF flow velocities will then be used for analysis (see details below *Statistical Analysis*).
- The respiration frequency band and the cardiac frequency band will be defined based on the two main distinct peak amplitudes of the frequency spectrum of the averaged CSF velocity waveforms measured with RT-PCMRI.
- The relative contribution of the respiration versus cardiac component of the CSF velocity waveforms will then be quantified by defining a power ratio between respiratory component and the cardiac component.

Respiration and ECG data:

- The pulse ox and respiration data collected during the RT-PCMRI acquisitions will be filtered using a 4th order Butterworth to extract only the respiration and only cardiac component.

Wearable device:

- Respiration data from wearable device collected during the 8-week intervention will be analyzed for the respiration rate and peak-to-peak respiration intervals. If collected, sleep data measured with wearable device will be analyzed to measure the influence of intervention on participants' long-term

sleep patterns objectively.

Self-report questionnaires:

- Response to self-report questionnaires will be analyzed for the statistical analysis to compare the changes in subject's quality of life, sleep, and existing stress levels.

Statistical Analysis

- The major dependent variables will be i) CSF flow metrics maximum and minimum (values of average CSF velocities; relative ratio of respiration vs. cardiac component of the CSF velocity; ratio of the maximum CSF velocity during breathing practices to the average of peak CSF velocities at baseline during natural breathing, ii) respiration rate and peak-to-peak respiration intervals and iii) self-reported questionnaire results. The effects of the interventions on these variables will be tested in a multivariate analysis of variance with repeated measures to compare pre- and post-intervention. An alpha value of 0.05 will be used for statistical significance.

9) Privacy, Confidentiality and Data Security

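### Blood pressure and BMI are named as outcome measures but have no analysis, while questionnaire scores share the joint test with CSF flow and respiration and can weaken it

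*Combined protocol and SAP*

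**What the plan says.** Section 4 (Study Design, outcome measures) numbers four outcomes. The first three are in this sentence: "Outcome measures will be i) blood pressure, ii) body mass index (BMI), iii) CSF flow velocities measured with the non-invasive MRI technique". The fourth, and the status of the questionnaires, follow: "iv) physiological data from wearable devices. We will also review response to self-report questionnaires". Questionnaires therefore stand outside the numbered list in that section.

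Section 6 (Procedures) collects blood pressure, BMI, questionnaires and MRI before the intervention. It repeats the same set afterwards and calls the repeated set outcome measures. Table 1 places blood pressure, BMI and questionnaires at Visits 2 and 11. Six instruments are named: SF-36, PSQI, PSS, PANAS-X, PROMIS and CAMS-R.

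Section 8 (Data Analysis, Statistical Analysis) gives the analysed variables: "The major dependent variables will be i) CSF flow metrics maximum and minimum", with further CSF ratios, then "ii) respiration rate and peak-to-peak respiration intervals and iii) self-reported questionnaire results". The test is stated once: "The effects of the interventions on these variables will be tested in a multivariate analysis of variance with repeated measures", and "An alpha value of 0.05 will be used for statistical significance". Its questionnaire paragraph says responses will be used "to compare the changes in subject's quality of life, sleep, and existing stress levels". Blood pressure and BMI appear nowhere in section 8.

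**The concern.** There are two linked problems.

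First, the numbered outcomes and the analysed variables do not match. Two of the four section 4 outcomes are measured twice and then have no planned comparison, estimate or summary. A blood pressure finding could then be reported or left out once the data are known, with nothing in the plan to show which was intended.

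Second, section 8 puts the questionnaires into the same multivariate test as the variables that carry the hypothesis. The hypotheses in sections 2 and 4 concern sustained slow, rhythmical breathing and larger modulation of CSF dynamics; they say nothing about questionnaire scores. With about 20 subjects, each added variable takes a denominator degree of freedom from the joint test and spreads the signal over more dimensions. The plan does not say how many scores enter, so the sensitivity of its only test is undefined.

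**Working it through.** **Comparing the sections**

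| Measure | Section 4 | Section 6 | Section 8 |
|---|---|---|---|
| Blood pressure | Numbered outcome | Measured pre and post | No analysis |
| BMI | Numbered outcome | Measured pre and post | No analysis |
| CSF flow | Numbered outcome | Measured pre and post | Major dependent variable, in the MANOVA |
| Wearable data / respiration | Numbered outcome | Tracked over 8 weeks | Major dependent variable, in the MANOVA |
| Questionnaires | Reviewed, outside the list | Collected pre and post | Major dependent variable, in the MANOVA |

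The documents give no power, effect size or standard deviation, so there is no stated figure to reproduce. What follows is illustration.

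**Inputs from the documents.** 10 per arm (section 4), with up to 13 per arm possible (section 5a); alpha 0.05 (section 8); six instruments (section 6); CSF metrics and two respiration metrics (section 8).

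**Assumptions.**
- The test of interest is the arm-by-time effect, because section 4 frames the hypothesis against active control.
- There are 4 CSF variables: maximum velocity, minimum velocity, the respiratory-to-cardiac ratio, and the ratio of maximum velocity in practice to baseline peaks.
- Each questionnaire gives one score. The documents give no score count.
- The Mahalanobis distance D between the arms' mean change vectors is 1.5 and stays there as questionnaires are added, so they contribute no signal.

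**Formula.** With n per arm and p variables, Hotelling's T-squared gives F with p and 2n − p − 1 degrees of freedom and noncentrality (n/2) × D². For n = 10 this is 5 × 2.25 = 11.25; for n = 13 it is 6.5 × 2.25 = 14.625.

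| Variables in the test | p | df, n = 10 | Power, n = 10 | df, n = 13 | Power, n = 13 |
|---|---|---|---|---|---|
| CSF + respiration | 6 | 6, 13 | 0.49 | 6, 19 | 0.68 |
| + 3 questionnaire scores | 9 | 9, 10 | 0.33 | 9, 16 | 0.53 |
| + 6 questionnaire scores | 12 | 12, 7 | 0.21 | 12, 13 | 0.39 |

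**Sensitivity to D, n = 10.** At D = 1.2 (noncentrality 5 × 1.44 = 7.2) power is 0.32, 0.21 and 0.14 for p = 6, 9 and 12. At D = 2.0 (5 × 4 = 20) it is 0.77, 0.57 and 0.36. The direction is the same throughout.

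**Precision of a separate blood pressure comparison.** The 95% half-width for the between-arm difference in change is t(0.975, 18) × SD × √(2/10) = 2.101 × 0.447 × SD = 0.94 × SD. For an assumed SD of change of 8 to 12 mmHg, that is about 7.5 to 11.3 mmHg.

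**The case against.** The strongest reply is that section 8 alone specifies a test, so the tested set is the section 8 list and there is nothing to choose between. That stands. A reader might infer that the tested outcomes change with the section followed, or that the two lists could be merged into one larger test. The documents support neither: section 4 attaches no test to its list, and nothing proposes a merger. What remains is that two named outcomes have no analysis.

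A reader might also infer that PANAS-X, PROMIS and CAMS-R are left out, because the questionnaire paragraph mentions only quality of life, sleep and stress. That is not shown either. The dependent variable in the Statistical Analysis paragraph is questionnaire results without restriction, and the PROMIS domains are not specified, so they may fall within those topics.

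Three further points have weight:
- Section 6 already repeats questionnaires as outcome measures, so "We will also review response to self-report questionnaires" describes their status in section 4 only.
- Table 1 files blood pressure and BMI under vitals, section 6 uses vitals as a check before scanning, and calling the listed variables major leaves room for descriptive reporting of others. But section 4 still numbers these two as outcomes, and no such reporting is described.
- The power loss comes from section 8's own choice of variables and would exist without section 4. It also depends on the questionnaires adding no signal. If they raised D from 1.5 to 2.0, power with 12 variables and 10 per arm would be 0.36 rather than 0.21. That is still below the 0.49 for CSF and respiration alone at D = 1.5, and part of any significant result would then reflect questionnaires.

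**Conclusion.** The point holds in this form. Blood pressure and BMI are named and measured as outcomes but given no analysis, and questionnaire results share one multivariate test with the CSF and respiration variables that the hypothesis is about. CSF flow and respiration appear in both lists, so the hypothesis-bearing outcomes are not lost; only the sensitivity of their joint test is affected.

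Under the stated assumptions, removing the questionnaires moves power with 10 per arm from 0.21 (six scores) or 0.33 (three scores) to 0.49. With 13 analysed per arm it moves from 0.39 or 0.53 to 0.68. The exact figures depend on the assumed D, the one-score-per-instrument count, and added scores carrying no signal. The mismatch between the outcome list and the analysis depends on none of these. This is a change the sponsor should make, short of a flaw that invalidates the trial.

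**What to change.** 1. Use one outcome list, worded the same way, in sections 4, 6 and 8, with a stated analysis or a descriptive label for every item.
2. In section 8, limit the multivariate test to the CSF and respiration variables.
3. Analyse questionnaire scores outside that test as secondary or exploratory outcomes. Name the scores used; their ranking is the sponsor's choice.
4. Report the between-arm difference in change in systolic and in diastolic blood pressure, each with a 95% confidence interval, outside the multivariate test. Do the same for BMI, or label it descriptive in section 4.

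The cost is revised wording and a few table rows; the data are already collected at Visits 2 and 11. Questionnaires lose their status as major dependent variables, and the blood pressure intervals will be wide, so they should be presented as estimates rather than as evidence of no effect.

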CSF circulation. CSF, a clear colorless fluid secreted by the choroid plexuses, moves by bulk flow (*macrocirculation*) around the central nervous system (CNS), and ensures the health of the CNS⁶. Impaired CSF circulation can comprise the normal physiological functions of the CNS, which then may contribute to CNS diseases including neurodegenerative conditions⁷. Furthermore, CSF circulation plays a key role in maintaining glymphatic transportation of CSF (*microcirculation*). Recent research efforts^{8,9} have defined a "*glymphatic function*", a brain-wide clearance mechanism facilitates the clearance of solutes and metabolic wastes from the brain interstitium. Sleep and arousal state are critical regulators of glymphatic function, since CSF tracer influx and interstitial solute clearance are increased during both sleep and anesthesia compared to the wakefulness¹, which is associated with slowed amyloid beta clearance and more rapid amyloid plaque deposition². The impairment of glymphatic function underlies the development of CNS diseases in the aging brain remains unknown, so it is critical to better understand the complete mechanisms supporting CSF circulation in the human CNS by i) developing non-invasive approaches to measure CSF circulation, and ii) potentially identifying therapies that can regulate and enhance CSF circulation. For this aim, we recently developed novel non-invasive imaging approaches to quantify CSF dynamics ¹² and we aim to study YB as a potential therapy for regulating and enhancing CSF circulation.

4) Study Design

This study is the K99 phase of the NIH-NCCIH K99/R00 study K99AT010158.

Protocol. The study protocol consists of 20 healthy young subjects undergoing an 8-week intervention (10 subjects in arm 1 and 10 subjects in the active control arm 2), and outcome measures within a 2-week period of pre-and post-intervention. We will test the hypothesis that the yogic breathwork practice with sophisticated breathing practices, compared to active control will enable participants to sustain slow and rhythmical breathing patterns and create larger modulations in their CSF dynamics.

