We plan to recruit 20 healthy subjects (18-65 years; 10 for each of the two groups) from the Portland community through IRB approved flyers posted around the OHSU campus and the city, and advertised in local media. While we do not expect that any participants will voluntarily drop from the study, unavoidable circumstances may arise and we expect to retain enough participants to collect sufficient data on intervention development, decisions on the appropriateness of our instruments, and burden to participants. In order to assure we have sufficient qualitative and quantitative data for this proposed study and any potential lost-to-follow up, we may recruit 13 people for each arm.

b) Inclusion and Exclusion Criteria

Inclusion criteria: 18-65 years of age, able to provide their consent to be in the study, available and able to participate in study activities, who can lie in supine, able to walk 15 feet, who have no prior/current regular mind-body practice inducing breath awareness or training such as yoga, meditation, Ta-Chi, Qi-Gong; a compatible device for physiological data trackers.

Exclusion criteria: inability to provide informed consent, MRI contraindications, need for muscle relaxants or anti-anxiety drugs in order to tolerate MRI, history of neurological disorders, head trauma with loss of consciousness, craniospinal disorders, spinal injury, sleep disorders, allergic or respiratory disorders, major or uncontrolled psychiatric illness or major depression, lung and heart problems, any condition requiring the use of medication that acts on the brain like stimulants, sedatives current substance abuse issues, pregnancy or nursing.

Optimization Scans:

Inclusion criteria: 18-65 years of age, able to provide their consent to be in the study, available and able to participate in 1-hour MRI scan, who can lie in supine, able to walk 15 feet.

Exclusion criteria: inability to provide informed consent, MRI contraindications, need for muscle relaxants or anti-anxiety drugs in order to tolerate MRI.

c) Vulnerable Populations

This study (K99 or R00 phase) will not include any vulnerable populations. We will not collect any information about subjects' status as prisoners, and will actively exclude pregnant women, children, neonates, and adults lacking capacity to provide informed consent.

d) Setting

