- We will assess each subject's response to the following self-report questionnaires during their imaging visits: quality of life (Short-Form Health Survey; SF-36¹⁷), sleep quality (Pittsburgh Sleep Quality Index; PSQI¹⁸), perceived stress (Perceived Stress Scale; PSS¹⁹), Positive Affect Negative Affect Scale - Expanded (PANAS-X)²⁰, The Patient-Reported Outcomes Measurement Information System (PROMIS)²¹, and Cognitive and Affective Mindfulness Scale-Revised (CAMS-R)²². Additionally, we will assess subject's attitudes, expectancy and blinding towards the study.

Physiological Data Tracking:

- **Respiration:** Each subject will be provided with a wearable device in order for the study team to objectively track subject respiration, thus home practice, throughout the intervention. For this purpose, we will use a commercial off the shelf monitor (Spire³). Study staff will assure that these devices remain free of potential identifiers. We will create a respiration tracker account for each user. Subjects will receive instructions on how to utilize the wearable device during the first imaging session.
- **Sleep:** A sleep tracking methodology may be implemented within the study to investigate the effects of the intervention on long-term sleep patterns – using a Fitbit tracker. Study staff will assure that these devices remain free of potential identifiers, and will create a sleep tracking account for each subject. Subjects will receive instructions on how to utilize the wearable device during the first imaging session.

Randomization. Subjects will be told they will be enrolled in one of the 8-week intervention groups for a set of breathing practices. Group allocation will be performed through a sex and age-based randomization by a study team member who will inform the subjects with which group they will be enrolled in. Neither the subject nor the investigator can choose which group the subject will be in. Subjects will be instructed and reminded not to reveal what group they are in during the study assessment visits. They will be instructed to ask the investigator if they have any questions about this kind of study.

i. 8-week interventions.

Breathing practices:

- The yogic breathwork protocol will incorporate breathing practices that will create slow deep rhythmical and large CSF flow patterns. Active control protocol will include slow breathing practices.

Interventions:

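### Arms are allocated by sex and age, but the analysis statement includes neither and names no arm-by-time term; if both factors are balanced and predict the change, the between-arm test is conservative.

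*Combined protocol and SAP*

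**What the plan says.** Section 6, under Randomization, states: "Group allocation will be performed through a sex and age-based randomization by a study team member". It does not say whether this means stratified blocks, minimisation or matching, and it gives no age bands.

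Section 4 (Protocol paragraph) sets a between-arm hypothesis: "We will test the hypothesis that the yogic breathwork practice with sophisticated breathing practices, compared to active control".

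Section 8 (Statistical Analysis) holds the only model: "The effects of the interventions on these variables will be tested in a multivariate analysis of variance with repeated measures", comparing before with after at alpha 0.05. Neither arm nor an arm-by-time term is named, and sex and age appear nowhere in that section.

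On size, section 5a says "We plan to recruit 20 healthy subjects (18-65 years; 10 for each of the two groups", and adds that "we may recruit 13 people for each arm" to allow for losses. Section 4 describes the participants differently: "The study protocol consists of 20 healthy young subjects undergoing an 8-week intervention".

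Respiration has two sources. Section 8 says of the scanner recordings: "The pulse ox and respiration data collected during the RT-PCMRI acquisitions will be filtered using a 4th order Butterworth". Of the wearable it says: "Respiration data from wearable device collected during the 8-week intervention will be analyzed for the respiration rate and peak-to-peak respiration intervals".

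**The concern.** Balancing the arms on variables that predict the outcome makes the arm difference less variable. If the model then omits those variables, their contribution stays in the error term. The reported standard error describes a less well-balanced trial than the one that was run, so intervals are too wide and the test rejects too rarely under the null. With 10 per arm, precision is scarce.

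The scope is limited. For an outcome measured before and after, a constant sex or age difference in level cancels in the change. Only an association with the 8-week change matters. For a measure with no baseline, an association with its level matters instead. A pre-versus-post test pooled over both arms is unaffected.

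**Working it through.** **Inputs from the documents.** 20 subjects, 10 per arm, possibly 13; alpha 0.05; allocation by sex and age. There is no power calculation, effect size or standard deviation, so there is no figure of the plan's own to reproduce.

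**Assumptions.** The test is two-sided. R² is the share of variance in the change explained by sex and age together, tried at 0 to 0.30. Age is spread evenly over 18–65. For power, the true difference is 1.32 SD, which gives 80% with 10 per arm.

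**Formula.** For one outcome and two time points, the arm-by-time test is the two-sample t-test on the change. Take the variance of the change as 1.
- Variance reported without sex and age: about 1/10 + 1/10 = 0.2.
- True variance under perfect balance: 0.2 × (1 − R²).
- Reported over true standard error: 1/√(1 − R²), which is 1/√0.90 = 1.054, 1/√0.80 = 1.118 and 1/√0.70 = 1.195.

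**Simulation, 10 per arm.** Excess of the reported over the true standard error, without sex and age:

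| R² | Exact 1:1 within four sex-by-age strata | Blocks of 4, random strata sizes | No balancing |
|---|---|---|---|
| 0.10 | 6% | about 4% | none |
| 0.20 | 10–11% | 8–9% | none |
| 0.30 | 15–18% | 12–13.5% | none |

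Ranges are differences between simulation set-ups. At R² 0.10 one blocks-of-4 run gave 3%. With exact balance the actual type I error is 0.039 at R² 0.10, 0.030–0.033 at 0.20 and 0.022–0.025 at 0.30. Without balancing it stays at about 0.05, so the effect comes from the balancing.

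**What adjustment changes.** With exact balance at R² 0.20, the estimate has an SD of 0.406 unadjusted and 0.402 adjusted, which is almost the same. The 95% interval half-width falls from 0.936 to 0.841 SD (0.841/0.936 = 0.90, so 10% narrower). The gain is therefore mainly a correct standard error.

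Power at 1.32 SD, without and with sex and age:
- R² 0, exact balance: 80% and 78%.
- R² 0.10, exact balance: 80% and 82%.
- R² 0.20: about 81% and 86–87%, depending on how tightly the allocation balances.

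**Break-even.** The loss of two degrees of freedom moves the critical t from 2.101 (18 df) to 2.120 (16 df). Under perfect balance this alone needs R² of 1 − (2.101/2.120)² = 0.018. Simulated break-even R² is about 0.025 with exact balance, 0.05 with blocks of 4 and 0.12 with no balancing.

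**Form of the adjustment.** In an example data set, the arm-by-time standard error was 0.386 without sex and age and 0.386 with their main effects only. Their by-time interactions reproduced the covariate-adjusted analysis of the change exactly (16 df).

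**Joint tests.** Counting four CSF metrics, two respiration variables and six questionnaires gives 12 outcomes. Power of one joint test on the changes (exact balance, assumed correlation 0.3 between outcomes):

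| Setting | Without sex and age | With |
|---|---|---|
| 12 outcomes, R² 0 | 80% | 64% |
| 12, R² 0.10, all affected alike | 72% | 69% |
| 12, R² 0.20, all affected alike | 63% | 74% |
| 12, R² 0.20, one affected | 81% | 65% |
| 4 outcomes, R² 0 | 80% | 77% |
| 4, R² 0.20, all affected alike | 71% | 87% |
| 4, R² 0.20, one affected | 81% | 80% |

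**Sensitivity.** With 13 per arm and exact balance, adjustment changes the single-outcome interval by +0.9% at R² 0, −11% at 0.21 and −17% at 0.31. If the sample is young (ages 18–35, same effect per year), gains of 8% and 14% shrink to 5% and 9%.

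**The case against.** **The planned analysis may be one joint test.** Read literally, section 8 puts all outcomes into a single multivariate analysis. There, adjustment loses power in three of the four 12-outcome settings above. The count of 12 is itself uncertain: with only quality of life, sleep and stress from the questionnaires it is 9, and the loss at R² 0 is from 80% to about 72%. This stands, and the covariates should be kept out of such a test.

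**The larger gap is the missing arm term.** A one-sentence statement that omits even arm is weak evidence that covariates were deliberately excluded. This also stands. The plan specifies no between-arm standard error. The point concerns the arm-by-time test that the section 4 hypothesis requires.

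**The gain may be negligible.** At R² 0.10 it is about two points of power, and nothing in the documents shows that sex or age predicts any change. This is fair, and it keeps the point modest.

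**Readings that go too far.** A reader might infer that omitting the allocation factors biases the comparison or inflates false positives. It does neither. A reader might also take the exact-balance figures (11%, 18%, break-even 0.025) as general, but the allocation method is not stated and looser balancing gives smaller effects. Finally, one might infer that wearable respiration certainly has no baseline. Table 1 marks tracking only at Visits 3–10, and section 8 places it within the intervention. Yet section 4 lists wearable data among the outcome measures, sections 4 and 6 place outcome measurement before and after the intervention, and the device is handed out before it starts. The documents do not settle this.

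**Conclusion.** The point holds as a conditional and modest one. The allocation factors do not reach the analysis, and the between-arm hypothesis has no named test. If sex and age are balanced and predict the change, a single-outcome arm-by-time test without them overstates its standard error by about 4–6% at R² 0.10, 8–11% at 0.20 and 12–18% at 0.30. If they predict nothing, or if the allocation does not balance them, there is no conservatism. These figures rest on assumed R², strata and age spread, because the documents supply none of them. The change is worth considering because it is cheap for single-outcome tests. Naming the arm-by-time term is worthwhile whatever R² is.

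**What to change.** Add to section 8, Statistical Analysis:

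> The between-arm hypothesis is tested for each CSF, respiration and questionnaire outcome by the arm-by-time term, with sex and age (continuous) included with their by-time interactions (equivalently, as covariates of the change score). Any outcome without a pre-intervention value is compared between arms with sex and age as covariates. Any joint multivariate test of all outcomes is run without these covariates.

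Main effects of sex and age alone are not enough, because they leave the arm-by-time standard error unchanged. Sections 4, 6 (including Table 1) and 8 should be reconciled on whether wearable respiration has a pre-intervention value. Respiration recorded during the two scans keeps its before/after analysis.

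**Cost.** Three sentences, no new data, and two error degrees of freedom (16 instead of 18). If sex and age explain nothing, the single-outcome interval is about 1.4% wider with exact balance (0.940/0.927), 2.5% with blocks of 4 and 7% with no balancing (0.992/0.927). Power then falls from 80% to 78% with exact balance and to 74% with none. Keeping the covariates out of the joint test forgoes a gain only where they affect most outcomes alike at R² near 0.20. Testing outcomes one by one also means that section 8 must say how the 0.05 level applies across them.
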